2.4.5.2.5 Sensitivity analysis for the computation of TGRL values

Two sensitivity analyses will be performed to assess the impact of the computation of TGRL values on the effect of treatment:

1. In the first sensitivity computation, TGRL will be computed from measured LDL-C only, not replaced by calculated LDL-C in case of missing value of measured LDL-C.
2. In the second sensitivity computation, TGRL will be computed from fasting samples only, ie, non-fasting samples will be excluded from analysis.

For both sensitivity computations, the percent change from baseline to Weeks 12 and 24 (ITT and on-treatment estimands) will be assessed in the same way than for the main computation of TGRL, using the model described in [Section 2.4.5.2.2](#).

2.4.5.3 Multiplicity issues

In order to handle multiple key secondary efficacy endpoints, the overall type-I error will be controlled by the use of a sequential inferential approach. Statistical significance of the primary parameter at the 0.05 alpha level is required before drawing inferential conclusions about first key secondary parameter (refer to order in [Section 2.1.3.2.1](#)).

Inferential conclusions about successive key secondary efficacy parameters require statistical significance of the prior one. This fixed hierarchical approach will ensure a strong control of the overall type-I error rate at the 0.05 level.

No further adjustments will be made for other efficacy endpoints for which p-values will be provided for descriptive purpose only.

2.4.5.4 Additional efficacy analysis: region North America

Additional efficacy analyses on selected endpoints will also be replicated in the subgroup of patients of the region North America.

2.4.6 Analyses of safety data

The summary of safety results will be presented by actual treatment group. Summaries will be descriptive in nature. Safety analysis will be performed by diabetes type and in the pooled data.

General common rules

All safety analyses will be performed on the safety population as defined in [Section 2.3.2](#), using the following common rules:

- Safety data in patients who do not belong to the safety population (eg, exposed but not randomized or re-randomized patients) will be listed separately.
- The potentially clinically significant abnormality (PCSA) values are defined as abnormal values considered medically important by the Sponsor according to predefined criteria/thresholds based on literature review and defined by the Sponsor for clinical laboratory tests and vital signs (PCSA version dated January 2009 [[Appendix A](#)]).
- PCSA criteria will determine which patients had at least 1 PCSA during the TEAE period, taking into account all evaluations performed during the TEAE period, including nonscheduled or repeated evaluations. The number of all such patients will be the numerator for the on-treatment PCSA percentage.
- The treatment-emergent PCSA denominator by group for a given parameter will be based on the number of patients assessed for that given parameter in the TEAE period by treatment group on the safety population.

All measurements, scheduled or unscheduled, fasting or not fasting, will be assigned to analysis windows defined in [Section 2.5.4](#) in order to provide an assessment for Week 0 to Week 32 time points.

- For quantitative safety parameters based on central laboratory measurements, descriptive statistics will be used to summarize results and change from baseline values by visit and treatment group using analysis windows. Summaries will also include the last on-treatment value and the worst on-treatment value. The last on-treatment value is defined as the last value collected during the treatment period (see [Section 2.1.4](#)). The worst on-treatment value is defined as the nadir and /or the peak value during the treatment period according to the direction (minimum or maximum) of the abnormality as defined in the PCSA list.
- For exploratory purpose, all TEAEs will be described by SOC, HLTG, HLT and PT according to up-titration status, ie, according to whether the patients remained on the 75 mg dose or whether they were up-titrated to 150 mg. These analyses will be exploratory and descriptive (no formal comparison per dose) as it is expected that there could be inherent differences in the baseline characteristics between those patients titrating to 150 mg and those remaining on 75 mg. In order to reduce the bias of this analysis, the period before the up-titration time point (planned at Week 12) will be analyzed separately since only the dose 75 mg is proposed for this time period and consequently the early events occurring before Week 12 can only be attributed to this dose. Therefore the descriptive analysis per dose will include any safety events occurring from the first injection post Week 12 IVRS/IWRS transaction to the end of the TEAE period. Baseline characteristics of patients receiving each dose will be summarized.

2.4.6.1 Analyses of adverse events

Generalities

The primary focus of AE reporting will be on TEAEs. Pre-treatment and post-treatment AEs will be described separately.

If an AE date/time of onset (occurrence, worsening, or becoming serious) is incomplete, an imputation algorithm will be used to classify the AE as pre-treatment, treatment-emergent, or post-treatment. The algorithm for imputing date/time of onset will be conservative and will classify an AE as treatment emergent unless there is definitive information to determine it is pre-treatment or post-treatment. Details on classification of AEs with missing or partial onset dates are provided in [Section 2.5.3](#).

Adverse event incidence tables will present, the number (n) and percentage (%) of patients experiencing an AE by SOC, HLTG (when applicable), HLT (when applicable), and PT. Multiple occurrences of the same event in the same patient will be counted only once in the tables within a treatment phase. The denominator for computation of percentages is the safety population within each treatment group.

Sorting within tables ensures the same presentation for the set of all AEs within the observation period (pre-treatment, treatment-emergent, and post-treatment). For that purpose, the table of all TEAEs presented by SOC and PT sorted by the internationally agreed SOC order and decreasing frequency of PTs within SOCs (in the alirocumab group) will define the presentation order for all other tables unless otherwise specified. The tables of AEs by SOC, HLTG, HLT, and PT will be sorted by the SOC internationally agreed order and the other levels (HLTG, HLT, PT) will be presented in alphabetical order, unless otherwise specified.

Analysis of all treatment-emergent adverse events

The following TEAEs summaries will be generated for the safety population.

- Overview of TEAEs, summarizing number (%) of patients with any
 - TEAE;
 - Serious TEAE;
 - TEAE leading to death;
 - TEAE leading to permanent treatment discontinuation.
- Number (%) of patients experiencing TEAEs by primary SOC, HLTG, HLT, and PT;
- Number (%) of patients experiencing common TEAE(s) presented by primary SOC, HLT and PT (HLT incidence $\geq 2\%$ in any treatment group), sorted by SOC internationally agreed order and by alphabetic order for the other levels (HLT and PT);
- Number of patients experiencing TEAEs by primary SOC and PT, sorted by the internationally agreed SOC order and by decreasing incidence of PTs within each SOC (in the alirocumab group). This order will be applied to all other TEAEs tables by SOC and PT, unless otherwise specified;

- All TEAEs by treatment group regardless of relationship in one column and, in the same table, in a second column, related to IMP according to investigator's opinion by primary SOC, HLT, HLT and PT;
- All TEAEs by maximal intensity (ie, mild, moderate or severe), presented by primary SOC and PT, sorted by the sorting order defined above;
- The event rate per patient-year (the number of patients with an event in question divided by total patient-years) will be provided for all TEAEs by SOC and PT. For a patient with event, patient year is censored at time of first event; for patient without event, it corresponds to length of TEAE period;
- Kaplan-Meier curves will be provided, when appropriate, for time from first dose of double-blind IMP to the first occurrence of selected TEAEs as well as incidence rates at the time of analysis (Week 24 for the first step analysis, Week 32 for the final analysis). Hazard ratio versus placebo group and corresponding 95% CI will be given. Patients without any event will be censored at the end of the TEAE period. Selected TEAEs will be local injection site reactions, general allergic reactions, neurocognitive events, hepatic disorder events and TEAE related to any clinically significant signal that needs further characterization;

Analysis of all treatment emergent serious adverse event(s)

- All serious TEAEs by primary SOC, HLT, HLT, and PT.
- All serious TEAEs by treatment group regardless of relationship in one column and, in the same table, in a second column, related to IMP according to investigator's opinion, by primary SOC, HLT, HLT, and PT;
- The event rate per patient-year will be provided for all serious TEAEs by SOC and PT;
- All SAEs will be listed.

Analysis of all treatment-emergent adverse event(s) leading to treatment discontinuation

All TEAEs leading to treatment discontinuation, by primary SOC, HLT, HLT, and PT.

Analysis of groupings of adverse events including selected adverse events of special interest

- All grouping of TEAEs including AESI as listed in [Section 2.1.4.1](#) will be analyzed using selections defined in [Section 2.1.4.1](#). They will be presented by SMQ and PT (when selection is based on SMQs) or by SOC and PT (when selection is based on the e-CRF tick box or HLT/HLT). The summaries will be sorted by decreasing incidence of PT within each SOC/SMQ (in the alirocumab group).
- Overview of each AESI and grouping of hepatic disorder events will be presented, summarizing number (%) of patients with any
 - AE;
 - TEAE;
 - TEAE leading to death;
 - TEAE leading to permanent treatment discontinuation.

- In addition, the following variables will be tabulated for the local injection site reactions TEAEs:
 - Highest intensity of the event (mild, moderate, severe);
 - Mean duration;
 - Number of events divided by the number of double-blind IMP injections received;
 - Time from first double-blind IMP injection to first injection site reaction;
 - Number of double-blind IMP injections up to the first injection site reaction;
 - Description of the highest intensity of each symptom recorded in the specific e-CRF page with tables.
- Besides, description of symptoms and possible etiologies for general allergic reaction TEAE reported by investigator, will be presented.

Analysis of pre-treatment and post-treatment adverse events

- All pre-treatment AEs by primary SOC and PT, sorted by the internationally agreed SOC order and decreasing incidence of PTs (in the alirocumab group) within each SOC;
- All pre-treatment AEs leading to treatment discontinuation by primary SOC and PT, sorted by the sorting order defined above;
- All post-treatment AEs by primary SOC and PT, sorted by the internationally agreed SOC order and decreasing incidence of PTs (in the alirocumab group) within each SOC;
- All post-treatment SAEs by primary SOC and PT, sorted by the sorting order defined above.

Subgroup of patients with 2 consecutive LDL-C <25 mg/dL

- If applicable, similar summaries of TEAEs as those described previously will be also provided on the safety subgroup population of patients with 2 consecutive results of calculated LDL-C <25 mg/dL. Only TEAE for which it will be confirmed or unclear that they occurred, worsened or became serious the day or after the first level of calculated LDL-C <25 mg/dL will be considered.

Analysis of non-serious treatment emergent adverse events

- All non-serious TEAEs by primary SOC and PT presented in alphabetical order within each SOC with PT >5% in any treatment group.

Analysis of product complaints

- Number (%) of patients experiencing product complaints.
- Number (%) of patients experiencing product complaints associated with a TEAE.

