The objective of the present study is to assess the efficacy and safety of alirocumab in insulin treated patients with Type 1 or Type 2 diabetes who currently have an LDL-C ≥ 70 mg/dL (1.81 mmol/L) and who, at baseline, have required, in addition to lifestyle modification, statin treatment with or without other LMT in order to achieve their LDL-C treatment goal, or who are statin intolerant. There is interest in the impact of lipid lowering therapy on measures of glycemic control as evidence has accumulated and suggests that the use of statin therapy is associated with an increased risk of diabetes. This is particularly true for people with risk factors for diabetes. Despite an increased relative risk of diabetes with statin therapy, the absolute risk is quite small. On average, it has been estimated that treatment of 255 people over a period of 4 years will result in 1 additional case of diabetes.

When balancing the benefit of therapy, treating the same number of people would prevent 5.4 vascular events (36). While this risk impacts patients with previously undiagnosed diabetes, it suggests that lipid lowering treatment could modulate glycemia. In fact, evidence suggests that it may be transmembrane cholesterol transport that imparts the added risk as a reduced prevalence of diabetes has been found in patients with familial hypercholesterolemia as compared to patients without the disease (37). As a result, understanding the impact of alirocumab on glycemic control in patients with diabetes is of interest.

In the Phase 3 program, involving a total of 5293 study participants, limited information is available in patients with diabetes who are treated with insulin and in those patients with Type 1 diabetes. Focusing the target population on patients with Type 1 or Type 2 diabetes treated with insulin will provide additional information on this potential treatment group, both from an efficacy and safety point of view (concomitant use of insulin and a monoclonal antibody). In addition, this study will provide useful information on the use of alirocumab in patients already familiar with self-injection.

It should be noted that all patients, except those with statin intolerance, will be on the maximum dose/regimen of statin that is tolerated by the patient, based on the Investigator's judgment, with or without other LMT. Those patients who are on statins and/or other LMTs at randomization should continue the treatments unchanged throughout the study.

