1.4 STUDY PLAN

This is a Phase 3b study to assess the efficacy and safety of alirocumab administered by subcutaneous injection in insulin treated patients with Type 1 or Type 2 diabetes and with hypercholesterolemia at high CV risk not adequately controlled on maximally tolerated LDL-C lowering therapy.

[figure not shown]
The study consists of a screening period of up to 3 weeks, a double-blind treatment period of 24 weeks, and a safety observation period of 8 weeks.

Patients, unless they are statin intolerant, will be taking a stable, maximally tolerated dose of statin therapy with or without other lipid modifying therapies (LMT). Statin dose and dose regimen as well as dose and dose regimen of other LMT(s) (if applicable) should be stable throughout the entire study duration including for 4 weeks prior to the screening period, during the screening period, and from screening to randomization until the Week 24 visit. Patients should be on a stable diet for glucose and lipid management throughout the entire study duration from screening to the Week 24 visit. Patients should be receiving treatment for diabetes in accordance with local/regional standards of care. Concomitant medications, including glucose lowering treatments, should be kept to a minimum during the study, however, if considered necessary for the patient's welfare they may be given at the discretion of the Investigator, with a stable dose (when possible).

Alirocumab will be administered subcutaneously with a starting dose of 75 mg every 2 weeks (Q2W) for 12 weeks with a blinded up-titration to alirocumab 150 mg Q2W at Week 12 if the LDL-C at the Week 8 visit is ≥ 70 mg/dL (1.81 mmol/L). Patients who have an LDL-C < 70 mg/dL (1.81 mmol/L) at the Week 8 visit will continue with alirocumab 75 mg Q2W until the end of the treatment period.

The data on lipid parameters from blood samples will be masked after randomization. No attempts should be made by the Investigator or patient to have the patient's lipid values independently evaluated after randomization until after the Week 24 visit, except for the safety of the patient, as per the Investigator's judgment.

Patients will visit the study site at Weeks -3, 0, 8, 12, 20, and 24 with lab work at each visit; in addition a phone visit is scheduled at Weeks 4 and 32.

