 - selected using the company CMQ based on the 5 following high level group terms (HLGTs) “Deliria (incl confusion)”, “Cognitive and attention disorders and disturbances”, “Dementia and amnestic conditions”, “Disturbances in thinking and perception”, “Mental impairment disorders”.
 - In a second approach, neurocognitive events will be analyzed using the CMQ developed using the FDA grouping of events: the PTs “Amnesia”, “Amnestic disorder”, “Anterograde Amnesia”, “Behavioural and Psychiatric Symptoms of Dementia”, “Change in sustained attention”, “Cognitive Disorder”, “Confusional State”, “Delirium”, “Dementia”, “Dementia Alzheimer's type”, “Dementia with Lewy Bodies”, “Disorientation”, “Disturbance in attention”, “Executive dysfunction”, “Frontotemporal Dementia”, “Illogical Thinking”, “Impaired reasoning”, “Incoherent”, “Judgement impaired”, “Memory Impairment”, “Mental Impairment”, “Mental Status Changes”, “Mini Mental Status Examination Abnormal”, “Presenile Dementia”, “Retrograde Amnesia”, “Senile Dementia”, “Thinking Abnormal”, “Transient Global Amnesia”, “Vascular Dementia” and the LLTs “Mental State Abnormal Aggravated”, “Thinking Slowed”.

Analyses of allergic drug reactions, local injection sites reaction and neurologic events will also be provided using the drop-down on the e-CRF AE page as a second approach. All analysis described above as additional are not AESI, but AE groupings that will be explored.

In addition the following grouping of events will be provided:

- Hepatic disorder events, selected using SMQ “Hepatic disorder”;
- Diabetic complications, selected using HLGT “Diabetes Complications”, HLT “Diabetes Mellitus (incl subtypes)”, HLT “Carbohydrate tolerance analyses (incl diabetes)”, PT “Hyperglycaemia”, PT “Hyperglycaemic unconsciousness”, PT “Hyperglycaemic seizure”, and excluding PT “Blood glucose decreased” and PT “Glycosylated haemoglobin decreased”;
- Hypoglycaemia events using SMQ “Hypoglycaemia” (narrow only).

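### Every planned summary of hypoglycaemia stops at the first episode per patient, so a change in recurrence would appear in no planned table

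*SAP*

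**What the plan says.** SAP 1.4 describes a trial "in insulin treated patients with Type 1 or Type 2 diabetes". SAP 2.1.4.1 lists, among additional groupings that are not adverse events of special interest, "Hypoglycaemia events using SMQ" (narrow terms only).

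SAP 2.4.6.1 governs how that grouping is reported:

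- **Groupings:** "They will be presented by SMQ and PT (when selection is based on SMQs"), sorted by incidence.
- **Incidence tables:** "Multiple occurrences of the same event in the same patient will be counted only once in the tables within a treatment phase".
- **Rate:** "The event rate per patient-year (the number of patients with an event in question divided by total patient-years) will be provided" for all treatment-emergent events by system organ class and preferred term. A patient with an event contributes time only up to the first one.
- **Kaplan-Meier and hazard ratio:** time to first occurrence, for injection site reactions, general allergic reactions, neurocognitive events and hepatic disorders. Another event enters only if a signal calls for it.
- **Injection site reactions only:** "Number of events divided by the number of double-blind IMP injections received".

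Safety is descriptive (SAP 2.4.6), and Protocol 11.4.3 rules out formal inferential testing of safety data.

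**The concern.** Hypoglycaemia is a foreseeable repeat event when everyone is on insulin. If alirocumab altered how often affected patients have episodes, without altering how many patients are affected, none of the planned summaries would move. If it raised the episode rate in general, the planned summaries would move, but by less than the true ratio whenever some patients are much more prone than others.

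Safety and tolerability in insulin-treated patients is a primary objective (SAP 1.2.1). Protocol section 4 says the target population will add information "both from an efficacy and safety point of view (concomitant use of insulin and a monoclonal antibody"). At stake is whether the report can describe hypoglycaemia burden, rather than only who had a first episode and when.

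**Working it through.** **Inputs from the documents.** 500 patients at 2:1 give 500 × 2/3 = 333.3 and 500/3 = 166.7, which reproduces the SAP's 333 and 167. The last injection is at Week 22, so a completer's treatment-emergent period is 22 × 7 + 70 = 224 days, or 224/365.25 = 0.613 years. The documents give no hypoglycaemia rate, dispersion or effect size, so there is no planned figure to reproduce on this point.

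**Assumptions.** Episodes per patient over the period are negative binomial with mean μ and dispersion k (k = 0 is Poisson). The true alirocumab:placebo rate ratio is 1.5. A placebo mean of 1 corresponds to 1/0.613 = 1.63 episodes per patient-year.

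**Formulas.**

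- Share with any episode: p = 1 − (1 + kμ)^(−1/k), or 1 − exp(−μ) when k = 0.
- First-event rate as the SAP defines it: p divided by the area under the event-free curve, with the period scaled to 1. For k = 2 that area is (√(1+2μ) − 1)/μ, so the rate is μ/√(1+2μ).
- Variance of the log rate ratio using all episodes: (1/μ₁ + k)/333 + (1/μ₀ + k)/167.

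**Attenuation, placebo mean 1, k = 2.**

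- Any episode: 1 − 1/√3 = 0.423 against 1 − 1/√4 = 0.500. The risk ratio is 0.500/0.423 = 1.18.
- First-event rate: 1/√3 = 0.577 against 1.5/√4 = 0.750. The ratio is 1.30.
- All episodes: 1.50, by construction.
- With k = 0 the first-event rate is exactly μ, so its ratio is 1.50, with no attenuation.

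**Recurrence only.** Suppose 30% are affected in each arm, with 2 episodes each on placebo and 3 on alirocumab. The risk ratio is 0.30/0.30 = 1.00. The first-event rate ratio is also 1.00 if first episodes occur at the same times in both arms. The episode-rate ratio is (0.30 × 3)/(0.30 × 2) = 1.50.

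**Precision.** Power at two-sided 0.05 is used only as a yardstick, because no safety test is planned.

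| Placebo mean | k | Any episode | All episodes | Difference (points) |
|---|---|---|---|---|
| 0.15 | 0 | 43% | 42% | −1 |
| 0.15 | 2 | 30% | 33% | +3 |
| 0.15 | 4 | 22% | 27% | +5 |
| 0.3 | 2 | 37% | 48% | +11 |
| 0.5 | 2 | 40% | 59% | +19 |
| 1 | 2 | 38% | 71% | +33 |

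For the last row, the variance is 2.667/333 + 3/167 = 0.0260, the SE is 0.161, and z = 0.405/0.161 = 2.52. At mean 0.3 the gain falls from 11 points to about 9 with k = 1 and 3 with k = 0. At mean 2 with k = 2 it is about 46. A simulated log-rank test on first episodes at mean 1, k = 2 gave 42%, little better than the any-episode comparison.

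**Type 1 stratum.** With at most about 67:33 patients, mean 1 and k = 2, the variance is 2.667/67 + 3/33 = 0.131 and the SE is 0.36. A rate ratio of 1.5 would carry a 95% CI of about 0.74 to 3.05. Yardstick power is 20% with all episodes, against 11% for any episode.

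**The case against.** A reader might infer that hypoglycaemia is reported solely as a yes/no percentage. The SAP does not support that. It also plans a time-adjusted first-event rate by preferred term, a maximal-intensity table, rates for serious events and a listing of all serious events, and it allows Kaplan-Meier curves with a hazard ratio if a signal emerges. The first-event rate is the fairer comparator, and without heterogeneity it is not attenuated. These summaries still give no count of repeat episodes: the rate stops at the first event, and a listing of serious events is not a rate.

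A reader might also take the gain in power as large in general. It is not. It depends on episode frequency and on how much patients differ, and the documents give neither. Since safety is descriptive, power here only indicates precision.

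The objection on data quality stands as a limitation. Nothing says each episode is a separate adverse event record. Protocol 10.4.2 prefers a diagnosis or single syndrome, which leaves room to record recurrent hypoglycaemia as one event. The flow chart shows no hypoglycaemia log, and the insulin log records doses only. A count may partly reflect reporting habits, although reporting also affects the planned summaries.

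Finally, the SAP does not say why the grouping exists, the protocol rationale does not name hypoglycaemia, and it is not an event of special interest. Counting injection site reactions per injection does not commit the SAP to event counts elsewhere. It shows only that an event count is already used for one repeatable event.

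**Conclusion.** The point holds as a gap in description. No planned hypoglycaemia summary uses more than the first episode per patient, so a change confined to recurrence would appear in no planned table.

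For a general increase in episodes, the understatement is conditional. Under the assumed ratio of 1.5, mean 1 and dispersion 2, the plan would show 1.18 (risk ratio) or 1.30 (first-event rate ratio). With no differences between patients, the first-event rate would show the full 1.50. The precision gain ranges from nothing when episodes are rare (−1 to +5 points at mean 0.15) to large when they are frequent and concentrated in some patients (38% against 71% at mean 1, dispersion 2).

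The documents do not support saying that the plan would miss a hypoglycaemia signal, or that any planned conclusion is invalid. The change is worth making because it is cheap and bears on a primary safety objective.

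**What to change.** In SAP 2.4.6.1, add for the hypoglycaemia SMQ grouping, pooled and by diabetes type:

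- the total number of treatment-emergent episodes by arm;
- episodes per patient-year, using all episodes and the full treatment-emergent period;
- an alirocumab:placebo rate ratio with 95% CI from negative binomial regression, with log time as offset and diabetes type in the pooled model, labelled descriptive.

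Keep the n (%) table and the first-event rate. The SAP already plans a hazard ratio with CI for selected events, so an interval of this kind fits its descriptive framework.

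State three limits beside the table: counts rest on adverse event reporting, and recurrent episodes may have been recorded as one event; a few patients with many episodes can influence the rate; and the Type 1 estimate will be imprecise.

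The cost is a paragraph of SAP text and one table from records already collected, with no new data collection and no alpha.
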